### 4.2 Drug/Device Handling:

Brivaracetam or placebo will be compounded and dispensed by Rx Artisans Inc. The active drug will be placed without modification into the appropriate gelatin capsule. Each strength of active and placebo will have an identical capsule color (25mg Purple, 50mg Green, 100mg Blue) and inactive ingredients (microcrystalline cellulose and silica gel). Study investigators will send a prescription to the pharmacy and the pharmacy will dispense the appropriate study medicine. The study medicine will then be provided to research volunteers at UMN or via FedEx/courier delivery in the United States. Study staff will confirm with each participant by phone (or participant-preferred communication form including email, text, etc.) that the drug was received.

### 4.3 Biosafety: N/A

## MEDICAL PROTOCOL (HRP-590)

PROTOCOL TITLE: Brivaracetam to Reduce Neuropathic Pain in Chronic SCI: A Pilot Clinical Trial  
VERSION DATE: 03/18/2024

- 4.4 Stem Cells: N/A
- 4.5 Fetal Tissue: N/A

## 5.0 Procedures Involved

### 5.1 Study Design:

This is a multi-center randomized, double-blinded placebo-controlled pilot clinical trial. Each site (Swedish Medical Center/Craig Hospital, UMN) will enroll and study 20 adults, 18 years of age and older with SCI. [name] will serve as PI, and [name] will serve as Co-I at UMN (local site). MRI data analysis will be conducted by [name] (Harvard University). [name] will receive a deidentified dataset and will have no human subject interactions. Research activities at the Swedish Medical Center/Craig Hospital will be conducted under a separate IRB protocol at Craig Hospital.

Participants who meet the eligibility criteria will be randomly assigned to active drug (escalating brivaracetam dose to 100 mg twice daily for 3 months) or placebo based on a randomization schedule developed by our biostatistician. This is a simple computer generated 1:1 scheme that randomly assigns participants to arm A or arm B. Study participants, research coordinators, and study personnel involved in outcomes assessments and analyses will all be blinded. The drug will be provided by RxArtisans pharmacy in Wayzata, MN. The active and placebo capsules will have identical appearance and consistency. Treatment assignment will be known only to the investigational drug pharmacies (RxArtisans). We have registered this pilot study with National Institutes of Health (NIH) clinical trials registry, [www.clinicaltrials.gov](http://www.clinicaltrials.gov) (NCT04379011). The pilot data generated by this effort will be used to power a subsequent multi-center clinical trial.

### 5.2 Study Procedures:

Overview of study procedures/study interventions. All interventions and activities are summarized in Table 1 below and then described in detail in the subsequent text. Potential participants will undergo an initial screening for eligibility based on the criteria below. After giving informed consent, participants will be randomized. Eligible participants will be required to receive medical clearance from their primary care provider within one month of (prior to) the baseline appointment, including physical exam, health history, and lab work to confirm normal renal function, absence of liver cirrhosis, and absence of pregnancy.

## MEDICAL PROTOCOL (HRP-590)

PROTOCOL TITLE: Brivaracetam to Reduce Neuropathic Pain in Chronic SCI: A Pilot Clinical Trial  
VERSION DATE: 03/18/2024

Baseline testing includes a focused physical exam, mental health and health history, blood samples for batch analysis, and an MRI scan. These procedures can either take place at the study site or virtually, depending on participant preference. Those who choose to participate in the study virtually will not take part in the MRI or blood draw. For participants with contraindications to MRI, the MRI will not be completed. For participants who prefer not to undergo a research MRI, the MRI will be optional.

Research blood banking will also be optional.

Participants must see their primary care physician to determine if they are eligible to enroll in this study, including having their physician order lab work to confirm that they are not pregnant (for females/people of childbearing potential) and that their kidneys and liver function properly. Their insurance will be charged and they will be responsible for any associated copays or costs. The study drug, research banking lab, baseline and end-of-study physical examinations, and MRIs performed by the study will be paid for by the study.

For participants who recently had comprehensive metabolic panel done, medical record review of lab results can replace new screening labs if the blood labs were completed within one month of (prior to) the scheduled baseline appointment. If the participant is seeing a provider in-system, the study coordinator will pull labs from the medical record. If the participant is not seeing a provider in-system, the study coordinator will instruct the participant's physician to fax the lab report to the study coordinator. The instructions for faxing will be on the screening eligibility sheet the participant brings to their doctor's appointment and available to be emailed for the participant upon request.

CDE-recommended questionnaires relating to pain, mood, active suicidality, satisfaction with life, kinesiophobia, sleep quality, and community integration will be administered. Participants will then begin 3 months of active treatment (100 mg BID) or placebo. All participants will receive a medication diary to track study drug compliance and to record medication use. Blinded data collectors will perform weekly check-in calls to assess for medication-related adverse events including the PHQ-9 for changes in mood and suicidality. Reported AEs identified in these calls will be documented and immediately shared with the PI for review.

End of study assessments will be repeated 3 months after baseline testing and again 1 month after cessation of study medication (active/placebo).

Lab work will be repeated to confirm normal renal function, absence of liver cirrhosis, and absence of pregnancy in individuals of childbearing potential at the end of the study. Specimen collection and analysis will either occur at the Fairview Clinical Research Unit or with the participant's

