### **3.0 Study Endpoints/Events/Outcomes**

#### **3.1 Primary Endpoint/Event/Outcome:**

Our primary endpoints will be 1) safety as determined by number of drug related adverse events and assessed through weekly adverse event screening by phone, and 2) efficacy as determined by reduction in pain intensity assessed by the Brief Pain Inventory. We will use the clinically meaningful reduction in Brief Pain Inventory score of 1 point or more as the definition of “drug response” in this study.

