## MEDICAL PROTOCOL (HRP-590)

PROTOCOL TITLE: Brivaracetam to Reduce Neuropathic Pain in Chronic SCI: A Pilot Clinical Trial  
VERSION DATE: 03/18/2024

asked to verify by phone or email receipt of study drug and initiation of the treatment course.

Drug dosage will be individually titrated for each participant with a goal of 100mg BID according to the following dose escalation protocol that we use clinically: 50mg BID X 2 weeks followed by 50mg TID X 2 weeks followed by 100mg BID X for 48 days, as tolerated. Participants will be allowed to reduce the dose of brivaracetam if they experience unacceptable side effects defined as increased somnolence according to routine clinical practice with other drugs in this class used for pain.

In the case of intolerance at 50mg BID during dose escalation, the dose will be reduced to 25mg daily or 25mg BID. In the case of intolerance, the dose will be reduced down 1 step to last tolerated dose. For intolerance at 100mg BID, the dose will be reduced to 50mg TID. For intolerance at 50mg TID, the dose will be reduced to 50mg BID. A dose of 50mg BID or higher must be maintained to complete the trial.

Drug discontinuation at study completion will be done according to the following protocol we use clinically that will be initiated for 2 weeks after end of study testing: Reduction to 50mg BID X 1 week followed by 50mg daily X 1 week. For those at the highest study tolerated dose of 50mg BID, the dose will be reduced to 50mg daily X 1 week and then stopped. At the end of study participants will be asked to mail empty bottles for pill counts with self-addressed and prepaid packaging, and will review the medication diaries via phone. We will use the clinically meaningful reduction in Brief Pain Inventory score of 1 point or more as the definition of “drug response” in this study. University of Minnesota Investigational Drug Services (IDS) will register the study, while Rx Artisans will be dispensing the drug.

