#### 8.2 Exclusion Criteria:

- Progressive myelopathy secondary to posttraumatic cord tethering or syringomyelia
- Active use of drugs known to interact with brivaracetam: rifampin, carbamazepine, sodium oxybate, buprenorphine, propoxyphene, levetiracetam, and phenytoin.
- Brain injury or cognitive impairment limiting the ability to follow directions or provide informed consent
- Pregnancy or lactation
- Epilepsy or active treatment for seizure disorder
- Past or current suicidality
- Active treatment for psychiatric disease
- Drug addiction
- Moderate or heavy alcohol intake (up to four alcoholic drinks for men and three for women in any single day, and a maximum of 14 drinks for men and 7 drinks for women per week)
- Hepatic cirrhosis, Child-Pugh grades A, B, and C
- Impaired renal function
- Contraindications to brivaracetam or pyrrolidine derivatives including allergy
- Active clinically significant disease (e.g., renal, hepatic, neurological, cardiovascular, pulmonary, endocrine, psychiatric, hematologic, urologic, or other acute or chronic illness) that, in the opinion of the investigator, would make the patient an unsuitable candidate for this trial.
- History of malabsorption or other gastrointestinal (GI) disease that may significantly alter the absorption of brivaracetam
- Use of any investigational drug 30 days prior to enrollment in this study

People with contraindications to MRI including retained bullet fragments, noncompatible metal implants, and implanted devices such as non-MRI compatible baclofen pumps may still be eligible for the study; they will not participate in the MRI scans.

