### **13.0 Risks to Participants**

#### **13.1 Foreseeable Risks:**

There is a risk of drug intolerance including allergy, suicidal behavior and ideation, somnolence and fatigue, psychotic symptoms, irritability, depression, loss of coordination/balance, constipation, aggressive behavior, and anxiety. All participants and caregivers will be educated to notify the PI or a health care provider if mood changes or suicidal behavior are observed. There is the risk of lowered seizure threshold for rapid drug withdrawal without tapering. There is some discomfort with venipuncture and there is the possibility of swelling and bruising at the site. There is also a slight chance that individuals become dizzy or faint. There are potential risks of loss of privacy and confidentiality. All participants will be encouraged to contact the study coordinator, or an investigator regarding any side effects or adverse events that occur.

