### *15.1 Data Analysis Plan:*

For aim 1, the main outcome variables of interest include various dimensions of pain, mood (PHQ-9), life satisfaction (SWLS), resting state brain connectivity, and community integration (CHART-SF) measured at baseline and again at 3-months of treatment. Of particular interest is whether there is a difference in pain reduction from baseline to end of study between the treatment and control groups; this will be analyzed in this pilot with linear regression including terms for group and time and the interaction of group by time. We note that many of these instruments have bounded scores and we will include analyses that recognize these (via, e.g., non- linearities or recognize the bounds such as Tobit regression) Further exploratory analyses will examine the relationships (correlations) between changes in pain and changes in mood, life satisfaction, resting state brain connectivity, and community integration using linear regression.

For aim 2, we will use the same analytic approach we have refined in our 2 active rsfMRI studies. MRI data will be analyzed using the SPM12 based Conn toolbox 3 (Version 17f, Matlab R2018b). Preprocessing steps include realignment and unwarping, slice-timing correction, ART based identification of outlier scans for scrubbing, segmentation and normalization to MNI space, and 8 mm smoothing. Denoising steps include scrubbing, aCompCor, ICA-based denoising, Global Regression, and 0.008 to 0.09 Hz band-pass filtering). Three main comparisons will be evaluated: The effect of drug treatment on rsfMRI measures, the effect of pain intensity on rsfMRI measures (each via linear regression as in Aim 1), and the differences in rsfMRI measures between active drug responders and non-responders; this last will also be analyzed via linear regression; note, however, that this will be limited to those in the active group and people in the placebo group will not be included. First, we will evaluate region-of-interest (ROI) based functional connectivity in a set of anatomically defined regions known to be impacted in SCI and neuropathic pain: the periaqueductal gray, the bilateral thalamus, the amygdala, the hippocampus, the insula, anterior cingulate, the precentral and the post-central gyrus. Second, we will evaluate, on a voxel-by-voxel basis, amplitude of low frequency fluctuations (ALFF) and intrinsic resting state functional connectivity.

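### Suicidality is a listed drug risk screened every week, but no by-arm count of it is planned for the trial results

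*Combined protocol and SAP*

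**What the plan says.** Section 13.1 (Foreseeable Risks) states: "There is a risk of drug intolerance including allergy, suicidal behavior and ideation". Section 5.2 (Study Procedures) sets up the surveillance, in which blinded staff make "weekly check-in calls to assess for medication-related adverse events including the PHQ-9 for changes in mood and suicidality". Under the Suicide Protocol in the same section, an endorsement of active suicidality starts a crisis procedure and notification of the PI. The study drop criteria, also in 5.2, list suicidality among the reasons for removal.

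Section 3.1 defines the first primary endpoint as "safety as determined by number of drug related adverse events and assessed through weekly adverse event screening by phone". Neither 3.1 nor 5.2 says how relatedness is to be judged.

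Section 15.1 names the PHQ-9 once, as the mood measure, in a list that ends "community integration (CHART-SF) measured at baseline and again at 3-months of treatment". Sections 15.1 to 15.3 do not mention suicidality, the weekly PHQ-9 answers or the Visit 4 PHQ-9, and they give no method for adverse events. The between-arm tests named in 15.3 are for participant characteristics.

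**The concern.** Safety is one of two primary endpoints, and suicidality is the listed risk for which the protocol has a validated instrument, a weekly schedule and a crisis procedure. In a randomised trial the natural summary is the number of participants affected in each arm, regardless of cause, because randomisation makes case-by-case attribution unnecessary. The plan has only two routes by which suicidality can reach the results:

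- the count of events judged drug-related;
- a PHQ-9 mood comparison between baseline and 3 months.

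The first depends on an undefined judgement. The second does not use the weekly answers, and a participant removed for suicidality may have no 3-month value. Followed as written, the trial could observe more suicidality on brivaracetam than on placebo and publish neither count. The larger trial that this pilot is meant to inform would then be planned without that figure.

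**Working it through.** The documents give no event rate, power or sample-size figure for suicidality, so there is no stated number to reproduce. The check has two parts: tracing the data, then sizing what a count could show.

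**1. Where the data go**

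| Data collected | Source | Planned use in the results |
|---|---|---|
| Weekly PHQ-9 by phone | 5.2 | Only through events judged drug-related (3.1) |
| Suicide protocol activations | 5.2 | None stated |
| Removals for suicidality | 5.2, drop criteria | None stated; dropouts are documented (18.2) |
| PHQ-9 at baseline and 3 months | 15.1 | Mood outcome |
| PHQ-9 at Visit 4 | Revision history 6.0; Table 1 | None stated |

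**2. Collected against analysed**

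Section 4.1 gives the schedule as "50mg BID X 2 weeks followed by 50mg TID X 2 weeks followed by 100mg BID X for 48 days". That is 14 + 14 + 48 = 76 days, or 76/7 = 10.9 weeks. Adding the 2-week taper gives 90 days, or 90/7 = 12.9 weeks. So about 11 to 13 weekly screens are taken, against two PHQ-9 time points analysed.

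**3. Number on active drug**

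Allocation is 1:1 (5.1). Section 23.1 gives 20 participants study-wide, so about 10 active. Section 5.1 gives 20 at each of two sites, so 40 in total and about 20 active. Both readings are carried through.

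**4. Effect of restricting to drug-related events**

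Let *p* be the true proportion of active participants with suicidality and *q* the fraction of cases judged drug-related. Neither is in the documents; the values below are assumptions. The chance that at least one case is counted on active drug is 1 − (1 − *pq*)^*n*.

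| *p* | *q* | *n* = 10 | *n* = 20 |
|---|---|---|---|
| 10% | 1 | 65.1% | 87.8% |
| 10% | 0.5 | 40.1% | 64.2% |
| 10% | 0.25 | 22.4% | 39.7% |
| 20% | 1 | 89.3% | 98.8% |
| 20% | 0.5 | 65.1% | 87.8% |
| 20% | 0.25 | 40.1% | 64.2% |

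For example, with *p* = 10%, *q* = 0.5 and *n* = 10, 1 − 0.95^10 = 0.401.

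**5. What zero cases would show**

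The exact two-sided 95% upper limit for 0/*n* is 1 − 0.025^(1/*n*). This is 30.8% for *n* = 10 and 16.8% for *n* = 20.

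**6. Whether a test is useful**

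Fisher's exact test first reaches p < 0.05 at 5 v 0 under either reading:

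- 10 per arm: 2 × C(10,5)/C(20,5) = 504/15,504 = 0.033.
- 20 per arm: 2 × C(20,5)/C(40,5) = 31,008/658,008 = 0.047.

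For assumed rates of 20% v 5%, power is 2% with 10 per arm and 17% with 20. A descriptive count is the useful output, not a test.

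**The case against.** The strongest reply is that suicidality is already watched closely. Section 18.2 has every adverse event logged whatever its cause and dropouts documented. A medical monitor reviews all reported events monthly, and serious events and deaths are escalated with a written report. Section 12.3 keeps and analyses collected data unless the participant asks otherwise. The weekly calls are also the collection route for the primary safety endpoint itself. All of this stands. A reader might infer that suicidality is unmonitored or reported only if judged drug-related, and the documents do not support that. An excess might be noticed by the monitor, whom 18.2 describes as unblinded, although 5.1 limits knowledge of assignment to the pharmacy. None of these provisions, however, calls for a count by arm with a denominator in the results, and 12.3 names no method.

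A second reply is that section 15 gives no method for any adverse event, so this is one instance of a wider gap. That is fair, and the table proposed here can sit inside a general safety analysis. It merits separate mention because its data come from a scheduled instrument and need no attribution.

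Three further inferences are tempting and should not be drawn:

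- That ideation will be put down to pain. The documents do not say so, and its listing as a drug risk could push attribution the other way. Under blinding, misattribution would be expected to lower counts in both arms rather than selectively hide an excess on drug.
- That every on-trial endorsement is new because "Past or current suicidality" is an exclusion. Section 8.2 gives no instrument or threshold, and nothing requires a negative baseline PHQ-9 answer.
- That the mood analysis uses the PHQ-9 total. Section 15.1 does not name the score.

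**Conclusion.** The concern holds as a gap in the trial results, not in individual safety reporting. No by-arm count of suicidality is planned. The attribution-restricted endpoint is a weaker rule than an attribution-free count from data the protocol already collects.

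That conclusion rests on the text alone. The size depends on assumed rates: if half or a quarter of cases were judged drug-related, a 10% risk would leave at least one counted case with probability 40% or 22% (10 active), or 64% or 40% (20 active). How often attribution would fail cannot be known from the documents. It is also uncertain how many removed participants would lack a 3-month PHQ-9, since the documents do not say what is assessed at removal. The count would be imprecise at either sample size, which is a reason to show its interval and not a reason to omit it. The plan should be changed.

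**What to change.** Add to section 15.1, beside the primary safety endpoint, in a dated amendment ideally made before unblinding:

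> For each arm, and whatever the attribution, we will report the number and proportion of participants with (a) any activation of the suicide protocol or endorsement of active suicidality as defined in section 5.2, and (b) any positive response to the PHQ-9 suicidality item, at any weekly call or visit from first dose to Visit 4. Incident counts are restricted to participants negative on that item at baseline; any others are listed separately. All answers up to and including the one that led to removal are included. Exact 95% confidence intervals are given for each arm, with the number of calls completed or person-weeks of observation. The table is descriptive and no hypothesis test is made.

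Parts (a) and (b) are both needed because the protocol's trigger is active suicidality, which may be narrower than any positive answer. Exposure is needed because participants removed early have fewer calls, and unequal removal could mask a difference. The report should give the zero-event limits for the sample size reached.

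The cost is one paragraph, one table and wide intervals. The revision history for version 8.0 notes that enrolment is complete, and the weekly calls are already in the protocol, so no new collection is required. Nothing here alters the removal rules, the suicide protocol or dosing.

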## MEDICAL PROTOCOL (HRP-590)

PROTOCOL TITLE: Brivaracetam to Reduce Neuropathic Pain in Chronic SCI: A Pilot Clinical Trial  
VERSION DATE: 03/18/2024

primary care provider, based on participant preference. Participants will receive \$150 after baseline testing, \$150 after end of study testing sessions and \$50 after the 1-month post drug cessation follow-up to compensate them for their time and to assist with transportation.

Our primary endpoints will be safety (# of drug related adverse events) and efficacy (reduction in pain intensity assessed by the Brief Pain Inventory). We will use the clinically meaningful reduction in Brief Pain Inventory score of 1 point or more as the definition of “drug response” in this study. Secondary outcomes include change in mood, satisfaction with life, community integration, and brain resting state functional connectivity. All fMRI data will be deidentified and sent by secure server to Harvard Medical School for analysis by [name] (consultant) as is done in our ongoing collaborative studies (Effects of Ekso-assisted gait training on Bone Health and Quality of Life: A Randomized Clinical Trial, PI [name]).

*Suicide Protocol:* Endorsement of active suicidality on PHQ-9 will trigger the suicide protocol. 911 will be called in the event of a psychological emergency noted during a phone call (credible report of intent to harm oneself). Study staff will first ask to speak to another adult in the household. If none is present or comes to call, study staff will call 911 and remain on the line until first responders arrive. In the event of a non-emergent psychological situation (psychological distress in the absence of intent for self-harm), study staff will refer the participant to their PCP or the National Suicide Hotline ([name]). In either case, study staff will notify the PI immediately.

*Modified Brief Pain Inventory (BPI) – main outcome.* The BPI is a short self-assessment questionnaire that provides information on various dimensions of pain including how pain developed, the types of pain a patient experiences, and time of day pain is experienced, as well as current ways of alleviating pain [Cleeland and Ryan, 1994]. The BPI also consists of the VAS Pain scale, a simple 10-point scale (0 = “no pain”, 10 = “pain as bad as you can imagine”) measuring a patient’s worst pain and least pain, on average and at present time. The Brief Pain Inventory provides information on the intensity of pain (the sensory dimension) as well as the degree to which pain interferes with function (the reactive dimension). According to several previous studies on pain in spinal cord injury, the BPI is an effective measure [Bryce et al., 2007].

*International Spinal Cord Injury Pain Data Set.* This tool assesses average pain intensity in the last week using a 0-10 numerical rating scale. The 1-10

